#### Intervention Groups:

| Arms                                 | Assigned Interventions  |
|--------------------------------------|---|
| Experimental:
Healthy Middle Aged | Drug: Methylene Blue (USP grade, 282 mg oral, up to 12 weeks)
Phenazopyridine hydrochloride (97.5 mg oral, up to 12 weeks)             |
| Placebo: Healthy Middle Aged         | Drug: FD&C Blue # 2 (USP grade, 282 mg oral, up to 12 weeks)
Phenazopyridine hydrochloride (97.5 mg oral, up to 2 weeks)               |
| Experimental:
Healthy Elderly MB  | Drug: Methylene Blue (USP grade, 282 mg oral, once daily, up to 12 weeks)
Phenazopyridine hydrochloride (97.5 mg oral, up to 12 weeks) |
| Placebo: Healthy Elderly MB          | Drug: FD&C Blue # 2 (USP grade, 282 mg oral, up to 12 weeks)
Phenazopyridine hydrochloride (97.5 mg oral, up to 12 weeks)              |
| Experimental:
MCI MB              | Drug: Methylene Blue (USP grade, 282 mg oral, once daily, up to 12 weeks)
Phenazopyridine hydrochloride (97.5 mg oral, up to 12 weeks) |
| Placebo:
MCI MB                   | Drug: FD&C Blue # 2 (USP grade, 282 mg oral, up to 12 weeks)
Phenazopyridine hydrochloride (97.5 mg oral, up to 12 weeks)              |
| Experimental:
AD MB               | Drug: Methylene Blue (USP grade, 282 mg oral, up to 12 weeks)
Phenazopyridine hydrochloride (97.5 mg oral, up to 12 weeks)             |

Placebo:  
AD MB

Drug: FD&C Blue # 2 (USP grade, 282 mg oral, up to 12 weeks)  
Phenazopyridine hydrochloride (97.5 mg oral, up to 12 weeks)

**The daily 282mg of MB or place will be divided into three doses of 94mg each to minimize the risk for urinary irritation. A second pill of Azo will be taken during one of these doses.**

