**NCT number: NCT02380573**

**IRB Approval Date: 11-06-2015**

**Unique Protocol ID: HSC20150410H**

## Protocol Template Form

|                                |  |
|--------------------------------|--|
| Item 1 UTHSCSA Tracking Number | Cognitive and Functional Connectivity Effects of Methylene Blue in Healthy Aging, Mild Cognitive Impairment and Alzheimer's Disease |
|--------------------------------|--|

|  |  |
|--|--|
| Item 2 Abstract / Project Summary | Provide a succinct and accurate description of the proposed research. State the purpose/aims. Describe concisely the research design and methods for achieving the stated goals. This section should be understandable to all members of the IRB, scientific and non-scientific.
DO NOT EXCEED THE SPACE PROVIDED. |
|--|--|

**Purpose/Objectives:** The purpose of the current proposal is to test the hypothesis whether daily oral MB for two week period (and up to 12 weeks if subject decides to continue participation) will improve memory, attention, cognition and functional connectivity in healthy aging volunteers, mild cognitive impairment (MCI) and Alzheimer's disease (AD) subjects by using objective MRI readouts and standard neuropsychological tests.

**Research Design/Plan:** Adult volunteers will be studied using a randomized, double-blinded, placebo-controlled design. MB and Placebo arms will be included for healthy aging, MCI and AD groups. MB and placebo pills will be compounded into blue immediate release capsules. Each arm will also receive a pill of Azo (phenazopyridine hydrochloride) with each daily dose as urinary tract analgesic and to maintain coloration of the urine in both groups. Subjects will have MRI scanning on two different days, fourteen days apart. After visit #2 is completed, the subject will be given the option to continue the study for another 10 weeks.

**Methods:** This study will use a low-dose oral USP MB (282mg) daily over a two-week period and subjects will take drug daily for two weeks combined with an additional daily dose of 97.5mg of Azo. Subjects will take 3 pills of MB/placebo each day (1 with each meal (94mg of MB per pill) and 1 pill of Azo for 14 days.

Daily dose intake may be extended to 12 weeks after the initial follow up visit.

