|  | 
Step-by-Step Methods: 
 
Adult volunteers will be studied using a randomized, double-blinded, placebo-controlled design. Placebo arms will be included for healthy middle aged, healthy elderly, MCI and AD groups as controls. USP Methylene blue (MB) and placebo pills will be compounded into blue immediate release capsules. The subject will take 3 pills of MB or placebo (94mg per pill) three times a day with each meal. Placebo will be FD&C Blue # 2 which is a powder similar to the powder form of methylene blue. Each arm will also receive a pill of phenazopyridine hydrochloride (97.5 mg, marketed as Azo Standard) with each daily dosage. Phenazopyridine is a safe OTC product used for urinary discomfort that turns urine brownish. This drug will be given to both MB and placebo groups so that both show similar urine discoloration. This choice of administration is justified not only to maintain the blind procedure but because it would prevent any mild discomfort experienced by MB urinary excretion during chronic treatment. The subject, person administering the drug, and data analysts will not know whether the intervention is placebo or MB. The design will only be unblinded at the last steps when necessary. All subjects will be told that the pill they take may or may not cause urine/feces discoloration depending on individual's metabolism.
 
Step by Step:
The healthy elderly, MCI and AD subjects will be recruited from the Texas Alzheimer's Research and Care Consortium (TARCC). A neuropsychological battery of tests (eg. logical memory I, logical memory II, verbal fluency/COWA, Instrumental Activities of Daily Living (IADL), Global Depressive Scale (GDS), etc.) will be administered for all subjects before MRI study (2 month window).
 
Baseline MRI scan will be performed during visit 1.
 
Subject will be given labeled pill organizers with pills to take on days 1 through 14. Subject will be contacted via telephone on days 3, 7 and 11 (<math>\pm 2</math> days) to document any adverse event or problem. After 2 weeks <math>\pm 3</math> days of MB (282 mg, oral x 14 days) or placebo, another neuropsychological tests and MRI scan will be obtained. On visit 2, the subject will be given the option to continue for another 10 weeks. During visit 3, after 10 weeks <math>\pm 3</math> days, the subject will complete the subset of neuropsychological tests completed in visit 1, and some of the MRI scans completed in visit 1.
 
For MRI, task-evoked BOLD fMRI, cerebral blood flow (CBF), resting-state fMRI, and CBF will be performed. For the task-evoked BOLD fMRI, subjects will perform the following scans while in the
 |

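### One of eight arms (healthy middle-aged placebo) lists phenazopyridine for up to 2 weeks where every other arm has 12; the cell conflicts with the masking rule and must be reconciled

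*Combined protocol and SAP*

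**What the plan says.** The Intervention Groups table in Item 6 has eight rows: an MB arm and a placebo arm for each of four populations. For Placebo: Healthy Middle Aged, the capsule line reads "Drug: FD&C Blue # 2 (USP grade, 282 mg oral, up to 12 weeks" and the phenazopyridine line reads "Phenazopyridine hydrochloride (97.5 mg oral, up to 2 weeks". In the other seven rows the phenazopyridine line reads "Phenazopyridine hydrochloride (97.5 mg oral, up to 12 weeks".

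The Step-by-Step Methods in Item 6 state the general rule: "Each arm will also receive a pill of phenazopyridine hydrochloride (97.5 mg, marketed as Azo Standard) with each daily dosage". They also give the reason: "This drug will be given to both MB and placebo groups so that both show similar urine discoloration". The same paragraph ties this choice to keeping the study blinded. It makes no exception for any arm and sets no separate period for phenazopyridine.

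The abstract (Item 2) likewise gives the drug to each arm "with each daily dose as urinary tract analgesic and to maintain coloration of the urine in both groups". Its Methods paragraph describes the two-week regimen as including the capsules "and 1 pill of Azo for 14 days", and then adds: "Daily dose intake may be extended to 12 weeks after the initial follow up visit". It does not say whether Azo, the marketed phenazopyridine product, continues in the extension.

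**The concern.** Phenazopyridine is in this trial partly as a masking device. MB colours urine, and the protocol relies on giving a second colouring drug to both arms so that the colour does not reveal the assignment. A masking drug does this only while both arms of a comparison receive it.

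The table gives the two healthy middle-aged arms different periods for that drug. If the placebo cell were followed, a middle-aged placebo subject who chose the extension would take blue capsules without the masking drug after week 2, while an MB subject in the same population could still be taking it. Two things would be at stake for that population at week 12: the strength of the blind, and the equality of the arms in a co-medication. Several week-12 measures are behavioural or neuropsychological, where knowing the assignment could matter.

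**Working it through.** The plan gives no figure to reproduce on this point. The check is a row-by-row reading of the table, set against the narrative.

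**Maximum durations in the Intervention Groups table (weeks)**

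| Population | Capsules, MB arm | Capsules, placebo arm | Phenazopyridine, MB arm | Phenazopyridine, placebo arm | Difference in phenazopyridine |
|---|---|---|---|---|---|
| Healthy middle-aged | 12 | 12 | 12 | **2** | **12 − 2 = 10** |
| Healthy elderly | 12 | 12 | 12 | 12 | 0 |
| MCI | 12 | 12 | 12 | 12 | 0 |
| AD | 12 | 12 | 12 | 12 | 0 |

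Capsules are at 12 weeks in 8 of 8 arms. Phenazopyridine is at 12 weeks in 7 of 8 arms and at 2 weeks in 1 of 8. The odd cell disagrees with its own row's capsules, with its matching MB arm and with the other three placebo arms.

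**Against the narrative**

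- The Step-by-Step Methods attach phenazopyridine to the daily dose in every arm. They allow 10 further weeks of dosing after visit 2, with no exception for this arm. The cell is inconsistent with that rule.
- The note under the table, on splitting the daily amount and taking Azo with one of the doses, also makes no distinction between arms.
- The 14-day Azo wording in Item 2 covers all subjects in the first two weeks. It cannot account for a shorter period in one arm only. If two weeks were meant throughout, the other seven cells would need explaining instead.

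**What could be affected**

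- The difference of up to 10 weeks coincides with the optional extension, weeks 3 to 12. All arms agree over weeks 1 and 2, so the week-2 assessment is untouched.
- Within the extension, only the healthy middle-aged population has unequal arms (1 of 4).
- Visit 3 repeats only a subset of the neuropsychological tests and some of the scans.
- The Primary Outcome Measures list week 12 as well as week 2. Item 4 describes the primary fMRI measures as taken before and two weeks after MB. The Data Analysis Plan names no week-12 contrast and no contrast by population.
- The documents give neither the number of middle-aged subjects expected to extend nor the effect of a missing masking drug on guessing the assignment. No bias can be calculated.

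**The case against.** The strongest reply is that this is a slip of one character. The figures 2 and 12 differ by a single digit, the narrative already states the rule for every arm, and a digit lost in converting the PDF cannot be excluded. Nothing in the documents ranks the table above the narrative. The table is loosely worded elsewhere too: two of its eight rows say once daily, although the note beneath divides the daily amount into three doses. It is therefore weak evidence that staff would dose from this one cell. This objection stands as far as intent and likely practice are concerned. It does not remove the conflict: the cell is part of the list of interventions assigned to each arm and bears on the stated blinding procedure.

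The second reply is that the consequence needs a chain of conditions. The cell must be followed, the subject must be a middle-aged placebo subject who extends, and urine colour must be noticed and read as a clue. That also stands. A reader might infer that the blind is broken in this population at week 12. The documents do not support that. Subjects are warned that discoloration is possible but not certain, the documents do not say whether FD&C Blue # 2 colours urine, and they do not say who fills or sees the pill organizers. Nor does any section say that phenazopyridine affects fMRI or cognition, so the co-medication difference is a difference in exposure, not a demonstrated bias.

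A reader might also treat the 14-day wording in Item 2 as a second contradiction, or as proof that two weeks was intended. It is neither. It describes the initial period and leaves the extension open.

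**Conclusion.** The inconsistency is real and certain on the text: 1 of 8 arms differs from the other 7, from its own capsules, and from the rule in the Step-by-Step Methods. Its effect is conditional. Only if the cell were followed could the two middle-aged arms differ in the masking drug, for up to 10 weeks, which could weaken the blind at week 12 for subjects who extend. This rests on reading the table's durations as maxima and on the protocol's own statement that phenazopyridine serves the blind. Week 2 and the other three populations are unaffected.

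The point deserves correction because it sits in a treatment-assignment cell tied to the blinding procedure and costs almost nothing to put right. The documents do not establish that anyone was or would be unblinded, and they do not show which duration was intended.

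**What to change.** The sponsor should:

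1. Reconcile the phenazopyridine entry for Placebo: Healthy Middle Aged with the other rows of the Intervention Groups table and with the Step-by-Step Methods, and confirm the intended duration.
2. Reconcile the 14-day Azo wording in Item 2 with the same text, so that it is clear what applies in the optional extension.
3. Check that pharmacy supply matches the reconciled text.
4. If any subject was dosed according to the cell as written, report the difference in phenazopyridine exposure between arms alongside any middle-aged MB-placebo comparison at week 12.

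No view is given on which duration is right. The cost is one table entry, one clarifying phrase in the abstract and one supply check. The fourth step adds a line of reporting only if it applies. No visits, subjects or procedures are added.

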**OUTCOMES:**

**Primary Outcome Measures:**

Working memory task fMRI measures

[Time Frame: baseline, 2 weeks ± 3 days, 12 weeks ± 3 days]

Delayed Match to Sample Task behavioral (ie. correct number of responses) and fMRI measures will be acquired simultaneously

Episodic memory task fMRI measures

[Time Frame: baseline, 2 weeks ± 3 days, 12 weeks ± 3 days]

Face-Name Task behavioral (ie. correct recalls) and fMRI measures will be acquired simultaneously

Sustained attention task fMRI measures

[Time Frame: baseline, 2 weeks ± 3 days, 12 weeks ± 3 days]

Psychomotor vigilance task behavioral (ie. reaction time) and fMRI measures will be acquired simultaneously

Neuropsychological Battery

[Time Frame: baseline, 2 weeks ± 3 days, 12 weeks ± 3 days]

TARCC designed psychometric tests

**Secondary Outcome Measures:**

Cerebral blood flow MRI measures

[Time Frame: baseline, 2 weeks ± 3 days, 12 weeks ± 3 days]

Resting measurements will be used to assess response and CBF

**Tertiary Outcome Measures:**

Functional Connectivity (resting state) fMRI measures

[Time Frame: baseline, 2 weeks ± 3 days, 12 weeks ± 15 days]

fMRI measurements will be obtained while the subject rests in the scanner

CO2 challenge: Cerebral blood flow measurements will be acquired during a brief (3-5 minutes) inhalation of medical-grade 5% CO2 in air for fMRI signal calibration purposes.

[Time Frame: baseline, 2 weeks ± 3 days, 12 weeks ± 15 days ]

Data Analysis Plan: Statistical parametric analysis will be performed to generate activation maps using established fMRI software. Task-evoked changes in brain activities will be analyzed and contrasted between placebo and MB conditions. ANOVAs, paired t and 2-sample t-tests will be used in analyzing the reaction times and success/failure rates in the DMS, FNT and PVT, with blocks (pre-MB vs. post-MB) as a within-subject variable and treatment (MB vs. Placebo) as a between-subject variable. Paired t-test will be used for group comparison with  $p < 0.05$  (False Discovery Rate  $q < 0.05$ ) considered statistically significant.

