| 
Item 4
Purpose and rationale
Insert purpose, objectives and research questions/hypotheses here. If you cut and paste from another document, make sure the excerpted material answers the question
 | 
The purpose of the current IND proposal is to test the hypothesis whether daily oral MB for 2 to 12 weeks will improve memory, attention, cognition and functional connectivity in healthy middle aged, and healthy elderly as well as MCI and AD subjects by using objective MRI readouts and standard neuropsychological tests. subjects by using objective MRI readouts and standard neuropsychological tests. MRI readouts include evoked functional MRI (fMRI), cerebral blood flow (CBF), and resting-state functional connectivity fMRI (fcMRI). We will utilize a double-blinded, placebo-controlled phase II clinical trial.
 
MRI and neuropsychological tests will be administered over about 1.5 hours before oral MB, and again about 2 weeks after oral MB. The subject will have the option to continue for another 10 weeks after the completion of the first two weeks. The primary outcome measures will include fMRI readouts to assess episodic memory, working memory and sustained attention, respectively, before and two weeks after MB. Secondary outcome measures will include standard neuropsychological tests.
  |

|   |  |  |
|---|--|--|
| 
Item 5
Study Population(s) Being Recruited
 
In your recruitment plan, how many different populations of prospective subjects do you plan to target?
Provide number: 4
 | 
Identify the criteria for inclusion:
 | 
Identify the criteria for exclusion:
 |
|---|--|--|

|   |  |  |
|---|--|--|
| 
e.g., a population can be individuals with type 2 diabetes controlled with diet and/or a population of healthy controls. Or a population can be individuals attending an education program, etc.
 
List each different population on a separate row and provide a short descriptive label:
(e.g., normal-healthy, diabetics, parents, children, etc.)
 
To add rows use copy & paste
 |  |  |

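### The plan's only significance rule assigns the group comparison to a paired t-test, although methylene blue and placebo are given to different, unmatched people

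*Combined protocol and SAP*

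**What the plan says.** **Design.** Item 6, Step-by-Step Methods, describes a randomised, double-blind trial: "Placebo arms will be included for healthy middle aged, healthy elderly, MCI and AD groups as controls". The Intervention Groups table lists a separate placebo row for each population, for example "Placebo: Healthy Middle Aged". After about two weeks on MB "or placebo, another neuropsychological tests and MRI scan will be obtained", so both arms have values before and after treatment. No crossover or matching is described.

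**Analysis.** The Data Analysis Plan is one paragraph, printed after the tertiary outcomes. It says three things that bear on this point.
- Task fMRI: "Task-evoked changes in brain activities will be analyzed and contrasted between placebo and MB conditions". No test is named.
- Task behaviour: "ANOVAs, paired t and 2-sample t-tests will be used in analyzing the reaction times and success/failure rates in the DMS, FNT and PVT". The plan then sets out the two factors of this analysis: "blocks (pre-MB vs. post-MB) as a within-subject variable and treatment (MB vs. Placebo) as a between-subject variable". It does not say which of these tests decides.
- Significance: "Paired t-test will be used for group comparison with", at a threshold of p < 0.05 and q < 0.05 for the false discovery rate. No other significance criterion is given.

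**Outcomes.** Item 4 gives as primary the "fMRI readouts to assess episodic memory, working memory and sustained attention, respectively, before and two weeks after MB" and makes the neuropsychological tests secondary. The Primary Outcome Measures list makes the neuropsychological battery primary as well. Cerebral blood flow (CBF) is secondary and resting-state connectivity tertiary. The Data Analysis Plan mentions none of these last three.

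**The concern.** A paired t-test needs two measurements that belong together. In this design the only such pair is one person's values at two visits. MB and placebo values come from different people, so the test that carries the significance threshold cannot be the test of MB against placebo. The plan's own description of treatment as a between-subject factor says as much.

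The threshold decides what may be reported as an effect. If an analyst follows the sentence literally, a before-after change in the MB arm can meet the criterion with no reference to placebo. Memory and attention tasks are repeated after two weeks, so any retest gain would count towards the drug. FDR control does not remove this, because a retest gain is a real within-arm change and not a chance finding.

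**Working it through.** The plan states no sample size, effect size, SD or power, so there is no figure to reproduce. The check is of the text first, then of scale under assumed inputs.

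**Step 1: the two readings of the rule.**
- *MB versus placebo.* The sentence before the rule makes treatment between-subject, and the arms are separate people. No pairs exist, and any pairing would be arbitrary.
- *Before versus after within an arm.* Pairs exist and the test is valid for change over time. It does not test MB against placebo, so no significance rule is attached to the randomised comparison.

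**Step 2: scale of the within-arm reading.** Assumed: one outcome, normal changes with SD 1, two-sided 0.05, no drug effect, retest gain d in SDs of change. The rejection probability comes from the noncentral t with df = n − 1 and ncp = d√n.

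| n per arm | d = 0 | d = 0.3 | d = 0.5 |
|---|---|---|---|
| 10 | 5.0% | 13.6% (ncp 0.3 × 3.162 = 0.95) | 29.3% (ncp 0.5 × 3.162 = 1.58) |
| 20 | 5.0% | 24.7% (ncp 0.3 × 4.472 = 1.34) | 56.5% (ncp 0.5 × 4.472 = 2.24) |

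In the same settings a 2-sample t-test on change rejects in 4.8 to 5.2% (40,000 simulations), because a gain common to both arms cancels.

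**Step 3: scale of the cross-arm reading.** Both tests have ncp = δ√(n/2). They differ in degrees of freedom: n − 1 if paired, 2n − 2 if 2-sample. At δ = 0.8:
- n = 10: ncp = 0.8 × √5 = 1.79; power 35.9% paired (df 9), 39.5% 2-sample (df 18).
- n = 20: ncp = 0.8 × √10 = 2.53; power 67.0% paired (df 19), 69.3% 2-sample (df 38).

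Simulated type I error of the arbitrary pairing is 5.0% (n = 10) and 4.8% (n = 20). Two random pairings of the same data disagree on p < 0.05 in 13.6% and 9.3% of data sets at 0.8 SD, and in 4.1% and 2.7% with no effect.

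**Step 4: does the replacement test need population in the model?** Assumed: four populations pooled, 5 per arm in each, true effect 0.8 SD, and mean change rising by a fixed step from one population to the next (40,000 simulations).

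| Step (SD) | Power with population terms | Power without |
|---|---|---|
| 0 | 69.2% | 69.4% |
| 0.3 | 69.0% | 65.1% |
| 0.6 | 68.7% | 53.0% |

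Type I error with the terms is 4.8 to 5.2% (3, 5 or 10 per arm per population). Without them, at step 0.6, it is 1.8 to 1.9%, which is conservative. With equal numbers in every cell, population differences enlarge the residual variance but do not bias the treatment contrast. The terms protect power, not type I error.

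**Step 5: coverage of outcomes.** A valid between-arm test is named for task behaviour only. Task fMRI has an intended contrast without a test. The battery, CBF and connectivity have neither.

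**The case against.** The strongest defence is that the paragraph shows between-arm intent. It contrasts placebo with MB for task fMRI, and it names ANOVA and 2-sample t-tests beside the paired test for behaviour. One can match paired t to visit and 2-sample t to treatment and conclude that the last sentence concerns change over time, where a paired test is proper. The before/after label mentions MB, but it names a visit factor that covers both arms.

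Most of this stands. A reader might infer that the plan ignores placebo or means to judge efficacy on the MB arm alone; the stated contrast and the between-subject factor do not support that. A reader might also infer that the false-positive rate will be 14 to 57%. That range needs the within-arm reading, which is only possible, together with an assumed sample size and retest gain. Nor does cross-arm pairing inflate type I error.

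The defence does not rescue the rule. On the benign reading the paired test is valid, but the only significance criterion then belongs to a comparison that leaves out the control group, and none applies to MB against placebo.

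**Conclusion.** The rule is wrong as written. Across arms it has no valid pairs. Within an arm it does not answer the trial's question. Which was meant cannot be settled from the text.

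The size depends on the reading, and every figure rests on assumed inputs. Cross-arm pairing costs about 2 to 4 points of power (39.5 − 35.9 = 3.6; 69.3 − 67.0 = 2.3) and leaves the verdict dependent on the pairing chosen. The within-arm reading ranges from no excess, if there is no retest gain, to rejection in more than half of trials at 20 per arm and 0.5 SD. That the arms are unmatched is inferred from the absence of any matching in the text.

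It must be fixed, because it is the sole stated criterion for the primary outcomes and the correction is simple.

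**What to change.** Replace the last sentence of the Data Analysis Plan with:

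> MB is compared with placebo by a between-arm test of baseline-to-2-week change (the treatment-by-block interaction, equivalently a 2-sample test on change) for the task behavioural measures, task fMRI (second-level between-arm test on each subject's post-minus-pre map), the neuropsychological battery, CBF and resting-state connectivity. The significance rule (False Discovery Rate q < 0.05) applies to this test. Within-arm paired t-tests are descriptive only.

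In the behavioural sentence, name the same test as the deciding one.

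The sponsor should also state:
- **Pooling.** If the four populations are pooled, population and population-by-block are recommended in the model. If they are analysed separately, the same between-arm test is used within each, without those terms.
- **FDR family.** The set of tests to which q < 0.05 applies.
- **12 weeks.** Apply the between-arm test only to outcomes collected at visit 3, since Step-by-Step Methods limits that visit to a subset of the tests and some of the scans. Label it supportive unless the sponsor reconciles Item 4 (two weeks) with the Primary Outcome Measures list (which includes 12 weeks). Continuation is optional after two weeks of treatment, so a comparison among those who continue is not fully protected by randomisation.

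The cost is analysis-plan wording. Baseline and 2-week values, treatment and population membership are already collected.

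### The significance rule cites FDR q<0.05 but names no test family, so on the usual voxelwise reading the scalar primary measures are uncorrected, and on any other reading the verdict depends on the family chosen

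*Combined protocol and SAP*

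**What the plan says.** The only significance rule is the last sentence of the Data Analysis Plan in Item 6. It begins "Paired t-test will be used for group comparison with", gives p<0.05, adds "False Discovery Rate" q<0.05 in brackets, and ends "considered statistically significant". No FDR procedure, test family, testing order or single primary comparison is given there or elsewhere in the text provided.

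The same paragraph describes two kinds of analysis to which the rule might apply:

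- Imaging: "Statistical parametric analysis will be performed to generate activation maps using established fMRI software".
- Behaviour: ANOVAs, paired t-tests and two-sample t-tests "will be used in analyzing the reaction times and success/failure rates in the DMS, FNT and PVT".

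The Primary Outcome Measures list in Item 6 has four headings: working memory, episodic memory, sustained attention and the neuropsychological battery. Each of the three tasks carries a behavioural and an imaging measure, for example "Delayed Match to Sample Task behavioral (ie. correct number of responses) and fMRI measures will be acquired simultaneously" and "Face-Name Task behavioral (ie. correct recalls) and fMRI measures will be acquired simultaneously". Each heading has the time frame "baseline, 2 weeks ± 3 days, 12 weeks ± 3 days".

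Item 4 is narrower. It names fMRI readouts for the three tasks, before and two weeks after treatment, as primary, and makes the neuropsychological tests secondary. Item 5 gives four populations, and the Intervention Groups table gives each its own MB and placebo arm.

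**The concern.** An FDR level has meaning only over a stated set of tests. This paragraph supports at least two sets: the voxels in one map, or the endpoint-level tests across tasks, populations and visits.

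Voxelwise FDR is the plausible meaning in an fMRI plan. It limits false activations inside one map. It does nothing for reaction times, correct responses or battery scores, and nothing for the number of maps, populations or visits examined. The scalar primary measures would then be judged at 0.05 each.

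On an endpoint-level reading, the family could still be drawn after unblinding, and the list of significant findings would change with it. What is at stake is which results the trial may report as effects of MB.

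**Working it through.** The plan states a threshold and no derived figure, so there is nothing to reproduce beyond the per-test level of 0.05. The documents give no number of comparisons, so a range is shown.

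**Inputs**

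- Per-test level 0.05 and q = 0.05 (Data Analysis Plan).
- Primary measures: 3 (Item 4); 4 headings (Item 6 list); or 7 if behaviour and fMRI are counted separately for three tasks and the battery counts as one, 3 × 2 + 1 = 7.
- Populations: 4 (Item 5).
- Post-baseline visits: 1 (Item 4, week 2) or 2 (Item 6, weeks 2 and 12).
- Assumptions: Benjamini-Hochberg as the FDR procedure; separate tests by population in the rows so labelled.

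**Step 1. Unadjusted testing.** For m independent tests, P(at least one false positive) = 1 − 0.95^m, and the expected number is 0.05 × m.

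| Count | m | P(at least one) | Expected |
|---|---|---|---|
| Item 4 outcomes, populations pooled, week 2 | 3 | 0.14 | 0.15 |
| Item 4 outcomes by population: 3 × 4 | 12 | 0.46 | 0.6 |
| Item 6 headings by population, week 2: 4 × 4 | 16 | 0.56 | 0.8 |
| Item 6 headings by population, two visits: 4 × 4 × 2 | 32 | 0.81 | 1.6 |
| Item 6 measures by population, two visits: 7 × 4 × 2 | 56 | 0.94 | 2.8 |

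These rows apply to scalar tests, or to one fMRI summary per task, with no correction across them. The Item 4 rows concern fMRI readouts alone.

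**Step 2. Correlation.** Outcomes and visits share subjects; populations do not. A simulation used two-sided tests with equal correlation within each population and independence between populations:

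| m | correlation 0 | 0.5 | 0.7 |
|---|---|---|---|
| 12 | 0.46 | 0.41 | 0.37 |
| 32 | 0.81 | 0.68 | 0.57 |
| 56 | 0.94 | 0.82 | 0.68 |

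With perfect correlation inside each population there are in effect four tests: 1 − 0.95^4 = 0.19.

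**Step 3. One FDR rule, family unstated.** Under Benjamini-Hochberg, a lone small p-value passes if p ≤ 0.05/m. Take p = 0.01 with every other p above 0.05:

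- m = 4 (four headings, one population, one visit): 0.05/4 = 0.0125, passes.
- m = 16 (all populations, week 2): 0.05/16 = 0.0031, fails.
- m = 32 (both visits): 0.05/32 = 0.0016, fails.

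**Step 4. A declared family.** With Benjamini-Hochberg over one fixed family and no true effects, the simulated chance of any false declaration stayed between 0.049 and 0.052 for m from 3 to 56. The inflation in Step 1 therefore comes from leaving tests outside the rule.

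**The case against.** The strongest reply is that the bracket is simply shorthand for significance at 0.05, FDR-controlled. A reader might infer that the sentence sets two conflicting thresholds; the text does not support that, because on such a reading the bracket would have no function. Any Benjamini-Hochberg positive at q<0.05 also has p<0.05, so doubt attaches only to nominal positives that fail q<0.05. This part of the reply stands: it is one under-specified rule. It does not rescue the plan, since one FDR rule still needs a family.

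The second reply is that the large counts are not the plan's own. This also stands in part. The Data Analysis Plan names treatment and pre/post factors and does not say that populations are tested separately, week 12 is an optional continuation, and Item 4 supports as few as 3 to 12 tests. A reader might infer that dozens of primary tests are planned and a false positive is close to certain. The documents do not establish this: 32 and 56 are derived counts at the upper end, and correlation pulls their percentages down.

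Third, the threshold is attached to a paired t-test for group comparison, and this phase II plan has no formal success rule. That is fair. It also means that no threshold at all is tied to the ANOVAs or two-sample tests, which adds to the gap.

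**Conclusion.** The concern holds as an undefined FDR family. On the plausible voxelwise reading, the behavioural and battery primaries listed in Item 6 have no multiplicity control, and neither does the set of maps across tasks, populations and visits. The chance of at least one false positive then runs from 14% (3 tests) to 94% (56 tests) under independence. For the 32-test count it is 81%, or 57% to 68% at within-population correlations of 0.7 to 0.5. Those correlations are assumed, and the 12-, 32- and 56-test counts assume testing by population. If the battery contributes several scores, 56 is low.

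On the endpoint-level reading, error can be held near 5%, but only once the family is fixed. Until then, the same p=0.01 can be called positive or negative. Either way the plan needs a correction rather than extra detail, because following it as written can leave primary tests unadjusted.

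**What to change.** 1. Reconcile Item 4 with the Item 6 outcome list on whether the neuropsychological battery is primary. This sets the family size.
2. State that voxel-level FDR q<0.05 applies only within each activation map.
3. List one family of all scalar primary MB-versus-placebo comparisons at week 2 in all populations: task behaviour, one pre-specified fMRI summary per task and, if primary, the battery as a named score or listed scores. Apply Benjamini-Hochberg q<0.05 across it. Tested by population, this gives 6 × 4 = 24 comparisons without the battery, or 7 × 4 = 28 with it as one score; the smallest-p cutoffs are 0.05/24 = 0.0021 and 0.05/28 = 0.0018.
4. Report unadjusted p-values as descriptive, and label the optional week-12 tests exploratory.

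This keeps the plan's own q<0.05. Cutting to a single primary outcome in a pooled model would be a separate design choice and is not needed to repair the rule. No extra subjects, visits or scans are required. The cost is that fewer nominal p<0.05 results can be called significant, and week-12 results, now in the primary time frame, carry less weight. The fMRI summary for each task must also be fixed before unblinding.
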